### 9.2 Analysis Plan

All CT and MRI scans will be reviewed centrally through the University of Michigan Department of Radiology. The primary endpoint analysis will report the best response percent and corresponding 95% binomial confidence interval. Only those patients who have measurable disease present at baseline (an eligibility criterion), have received at least 11 weeks of therapy and have had their disease re-evaluated; or who come off therapy due to progressive disease or unacceptable adverse events at any time, will be considered evaluable for response. Each evaluable patient will be assigned one of the following categories: 1) complete response, 2) partial response, 3) stable disease, 4) progressive disease, 5) early death from malignant disease, 6) early death from toxicity, 7) early death because of other cause, or 8) unknown (not assessable, insufficient data). All of the patients who met the evaluability criteria will be included in the analysis of the primary endpoint. Patients in response categories 1-2 while on treatment will be considered responders to treatment. Thus, an incorrect treatment schedule or drug administration does not result in exclusion from the analysis of the response rate.

All patients enrolled and who receive any drug will be assessable for toxicity from the time of their first treatment with study drug. Toxicity will be described by grade and type using frequencies and percentages.

Serum thyroglobulin will be reviewed for the 12 months prior to enrollment, and will be obtained at enrollment and at  $12\pm 1$  and  $24\pm 1$  weeks of therapy. The changes in thyroglobulin before pioglitazone treatment and after treatment will be summarized overall and by response. Patient profile plots will be created to descriptively show the serum thyroglobulin values over time. Means and standard deviations or medians and minimum and maximums will be used to summarize all patients at each time and changes from baseline at the later times. Similarly, statistical descriptions of the response group and the non-response groups will be reported.

The changes in target lesion lipid content at  $24\pm 1$  weeks (or the end of treatment, whichever comes first), compared to pre-study, will be summarized overall and by response. Means and standard deviations or medians and minimum and maximums will be used to summarize the overall patient population at each time. Similarly, statistical descriptions of the response group and the non-response groups will be reported. A paired t-test (or paired Wilcoxon rank test if the data distribution requires it) will be used to compare the changes in target lesion lipid content after treatment to the baseline lipid content in the overall study population with both measurements. In an exploratory analysis, a logistic model will be used with the outcome being response and the independent predictor will be the lipid content change from baseline. The changes in target lesion radioiodine uptake will be summarized overall and by response in a follow-up protocol available to subjects completing this study.

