### **2.3 Correlative Studies Background**

Serum thyroglobulin levels will be measured. Thyroglobulin is a well established tumor marker in thyroid cancer. Serial serum thyroglobulin measurements are part of the accepted standard of care for thyroid cancer management (5).

Optional for enrolled patients who consent: MRI will be used to assess fat content of the cancer metastases. MRI is an accepted non-invasive method to assess tissue fat content. Our mouse tumor model data indicate that pioglitazone causes a lipogenic response (i.e. the mouse tumors accumulate lipid droplets), which reflects the PPAR $\gamma$ -like action of PPFP. To assess feasibility, we performed thyroid MRIs on two PPFP;Pten $\Delta$  mice that were treated with pioglitazone and two that were not. Thyroid fat content was 13% in the two control diet mice, and 25 to 26% in the pioglitazone-treated mice. This optional MRI consent will allow us to assess whether a similar effect occurs in patients, and will provide another index of a response to pioglitazone.

Optional for enrolled patients who consent: Unstained tumor tissue slides from archival paraffin blocks, and/or fresh biopsy of tumor metastases, and/or peripheral blood (sera and/or DNA) will be collected and stored for potential analyses of tumor markers that may predict response or insensitivity to pioglitazone.

Optional radioiodine scan, and potentially radioiodine therapy, at the end of pioglitazone therapy. In non-PPFP thyroid carcinomas, thiazolidinediones have been shown to induce radioiodine uptake in some patients with otherwise non-iodine avid metastases, although in general the level of uptake has been clinically insignificant (11, 12), with rare exception (13, 14). It seems unlikely that pioglitazone would induce clinically useful radioiodine uptake in PPFP carcinomas, since in the mouse model the thyroid cells differentiate toward adipocytes, not thyrocytes. However, radioiodine uptake in patients should be determined to formally address this question. Patients with clinically significant uptake would be considered for radioiodine therapy, if clinically appropriate. This will be addressed in a separate follow-up protocol available to subjects completing this study.

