# **7. CORRELATIVE/SPECIAL STUDIES**

## **7.1 Laboratory Correlative Studies**

Detection of the PAX8-PPARgamma fusion gene.

Eligibility requires that the tumor contain the PAX8-PPARgamma fusion gene. This will be assessed in specimens of the resected primary tumor or metastases obtained from all participating patients. Please see supplemental Lab Manual for procedures.

Optional MRI evaluation of tumor lipid.

Since pioglitazone induces lipid accumulation in the thyroids of the mouse model, we predict that pioglitazone will induce lipid accumulation in the metastases of patients. For patients who consent, tumor lipid content will be evaluated by MRI at baseline (any time after informed consent and before the first dose of pioglitazone), and at 24±1 weeks or the end of treatment, whichever comes first.

Optional fresh biopsy of metastasis.

For patients with biopsy-accessible metastases that meet RECIST criteria for measurable disease, optional fresh biopsies of the metastases may be obtained. Institutional procedures for procurement of fresh tumor biopsies will be followed. Biopsies should be obtained pretreatment (anytime after informed consent and before the first dose of pioglitazone) and also may be obtained within 1 day of the last treatment. The biopsy specimens will be analyzed for the PAX8-PPARgamma fusion gene per above, and will be stored for potential future analyses of biomarkers that may correlate with response to or lack of response to pioglitazone. For example, the expression of PPARgamma target genes may be analyzed.

Optional collection of sera.

For patients who consent, serum (up to 21 mL) may be collected pretreatment (anytime after informed consent and before the first dose of pioglitazone) and also may be collected within one day of the last treatment. Sera will be stored at -80C for potential future analysis of biomarkers that may correlate with response to or lack of response to pioglitazone.

Optional collection of peripheral blood DNA

For patients who consent, peripheral venous blood (up to 7 mL) will be collected for the isolation of DNA and the determination of DNA sequence. This may be compared to DNA extracted from the primary tumor or metastases to identify gene mutations or polymorphisms that may correlate with the development of the cancer and its response or lack thereof to pioglitazone.

Optional radioiodine scan and potential radioiodine therapy at the end of pioglitazone therapy.

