### 8.3 Other Response Parameters

Serum thyroglobulin will be reviewed for the 12 months prior to enrollment, and will be obtained at enrollment and at  $12\pm 1$  and  $24\pm 1$  weeks of therapy. The changes in thyroglobulin before pioglitazone treatment and after treatment will be summarized overall and by response. Serum thyroglobulin will not be used as a response parameter if endogenous antibodies invalidate the measurement.

Optional correlative study. MRI will be used to assess lipid content of target lesions pre-study, and at  $24\pm 1$  weeks or the end of treatment, whichever comes first. The changes in lipid content after treatment will be summarized overall and by response.

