## 9. STATISTICAL CONSIDERATIONS

### 9.1 Study Design

This is a phase II study with a primary endpoint of response (CR or PR per RECIST criteria) to pioglitazone therapy. Best response during the 24 weeks on Pioglitazone therapy will be assessed in thyroid cancer patients with metastatic disease who have CT evidence of disease progression in the prior 14 months. It is expected that without treatment there would be no improvement in the disease in these patients. This drug will be of interest to pursue alone or in combination with other therapies with a 40% best response rate. Accrual of 14 evaluable patients at a 95% two-sided significance level will provide 87% power to detect a 40% response rate compared to the expected 5% or less. A patient will be evaluable if they remain on treatment for 11 weeks or they are removed from study due to progression or toxicity.

Secondary endpoints include toxicity, serial measurements of serum thyroglobulin, lipid content of metastases determined by MRI, and radioiodine uptake. Since this drug is well known and used in humans we do not expect toxicity to be a problem. However, toxicity will be observed and reported throughout the trial as this is the first trial with Pioglitazone in this patient population.

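### The plan does not mask the lipid MRI read to time point or CT response, so a reading shift could not be told apart from a drug effect on lipid

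*Combined protocol and SAP*

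**What the plan says.** All references are to the combined protocol and SAP.

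- **Reading.** Section 9.2 states that "All CT and MRI scans will be reviewed centrally through the University of Michigan Department of Radiology". It says nothing on masking, reading order, number of readers or what a reader is shown.
- **Expected result.** Section 7.1 says "we predict that pioglitazone will induce lipid accumulation in the metastases of patients". Section 2.3 adds that the MRI "will provide another index of a response to pioglitazone".
- **Design of the comparison.** Section 8.3: "MRI will be used to assess lipid content of target lesions pre-study, and at" week 24 or the end of treatment. The trial has one arm.
- **Analysis.** Section 9.2: "A paired t-test (or paired Wilcoxon rank test if the data distribution requires it) will be used to compare the changes" with baseline. Lipid is also summarised by response group. A further step, labelled exploratory, reads: "a logistic model will be used with the outcome being response and the independent predictor will be the lipid content change from baseline".
- **Status.** Section 9.1: "Secondary endpoints include toxicity, serial measurements of serum thyroglobulin, lipid content of metastases determined by MRI, and radioiodine uptake". Section 1.3 lists the same lipid question as an optional correlative objective.
- **Sites.** Footnote j of the study calendar (4.7) has the baseline lipid MRI cover areas of measurable disease, and the follow-up MRI only those sites where lipid could be quantified at baseline.

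**The concern.** Central review makes readings consistent. It does not keep the reader from knowing which scan is the later one or how the patient has done. Three features make that matter here.

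First, there is no untreated group, so a tendency to read follow-up scans higher has nothing to cancel against. It goes straight into the mean change that the paired test compares with zero.

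Second, the protocol states the hoped-for direction in advance.

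Third, the department that reviews the CT scans for response also reviews the MRI scans that supply the predictor in the response model. If knowledge of the CT result influenced the lipid reading, an association would appear even if none existed.

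At stake is the step that carries the mouse mechanism over to patients. If the lipid result is positive and reading was not masked, no later analysis of the same readings can separate drug effect from reader expectation.

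**Working it through.** **1. The plan's own figure.** The documents give no power, SD or reader error for the lipid endpoint. The only design figure is the 87% power in 9.1 for the primary endpoint (14 evaluable patients, 40% against 5%). It reproduces with an exact binomial test that declares success at 4 or more responders of 14: P(X ≥ 4 | 0.05) = 0.0042 and P(X ≥ 4 | 0.40) = 0.876. Nothing below changes it.

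**2. Inputs for the lipid illustration.**
- Number of pairs, n: the MRI is optional and 9.3 accrues 15 patients, so about 15 is the ceiling. I use n = 10, with 6 and 14 as a check.
- Scale: the only lipid values in the documents are from four mice (2.3), 13% in two controls against 25 to 26% in two treated, a gap of 12 to 13 points.
- SD of within-patient change, s: not given. Assumed 2, 4 or 8 percentage points.
- Systematic reading shift at follow-up, b: not given. Assumed 1, 2 or 3 points.
- True lipid change: zero.

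**3. Formula.** The paired t statistic follows a noncentral t distribution with n − 1 degrees of freedom and noncentrality δ = (b/s)√n. The two-sided 5% test rejects with probability P(T > c) + P(T < −c), where c is the 97.5% point of the central t. For n = 10, c = 2.262.

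Worked case: b = 2, s = 4, n = 10 gives δ = 0.5 × 3.162 = 1.581 and a rejection probability of 29.3%.

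**4. Results, n = 10, no true change.**

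| Assumed SD of change | Shift 1 point | Shift 2 points | Shift 3 points |
|---|---|---|---|
| 2 | 29% | 80% | 99% |
| 4 | 11% | 29% | 56% |
| 8 | 6% | 11% | 19% |

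With no shift, every cell is 5%. At SD 4, the rates for shifts of 1 / 2 / 3 points are 8% / 17% / 32% with n = 6 and 14% / 41% / 74% with n = 14.

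**5. Link to response.** I use a two-sample t-test as a stand-in for the logistic model and give responders' readings an extra shift of 0.5 / 1.0 / 1.5 SD, with no true association. Here δ = shift / √(1/n₁ + 1/n₂), with the shift in SD units. With 6 responders and 8 non-responders (assumed split), the 5% test rejects 14% / 40% / 72% of the time; with 4 and 6, 11% / 28% / 53%.

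**6. Can the read be deferred?** The calendar has one follow-up lipid MRI, at week 24 or the end of treatment. Neither the duration rules in 4.3 nor the dose rules in section 5 use lipid. A read made after the follow-up scan therefore delays no treatment decision.

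**The case against.** The strongest reply is that this rests on silence. Several parts of it stand.

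- **A reader might infer that the plan has the MRIs read with time point and response known.** The documents do not say so. One department need not mean one reader, and the timing of the read is not given. Where a confirmatory CT is needed, it comes 4 or more weeks after the week-24 imaging (8.1), so final response may not be settled when the lipid MRI is read. The supportable statement is that the plan does not prevent an unmasked read.
- **A reader might infer that lipid content depends on where the reader places a region.** No sequence, quantification method or region rule is given; 2.3 says only that MRI is an accepted way to assess tissue fat. A largely automated measure would leave less room for judgement. The point is therefore conditional on some judgement being involved.
- **A reader might infer that the plan predicts a link between lipid change and RECIST response.** Section 7.1 predicts a rise in lipid. The link is at most implied by 2.3, and the model that examines it is labelled exploratory.
- **The size is assumed.** Both SD and shift are assumed, and the table runs from 6% to 99%. It shows that a shift could matter, not that one will occur.
- **Masking can be defeated.** Under footnote j the follow-up scan may cover fewer sites than baseline, which can reveal the order. Lesions that shrink by 30% or grow by 20% show their own history.
- **The consequence is limited.** The lipid MRI is optional, and no decision rule uses it.

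None of this removes the gap. Lipid is a listed secondary endpoint with its own test, and a single-arm before/after design gives no other protection against a reading shift.

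**Conclusion.** The point holds as a modest weakness in a secondary endpoint. As written, 9.2 leaves the lipid read unmasked to time point and CT response, in an uncontrolled before/after comparison whose direction is stated in advance. If the measurement involves reader judgement, a systematic shift would be indistinguishable from a drug effect.

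The size cannot be fixed from the documents. Only the direction, an error rate above the nominal 5%, is common to all the assumed cases. The response rate, its confidence interval and the 87% power are untouched. The change is worth making because it is cheap and because the fault cannot be repaired by reanalysing the same readings.

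**What to change.** Add to 9.2:

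> Lipid values used in the analysis come from one paired read per patient, made after the follow-up MRI within the central radiology department. The two scans are de-identified, cropped to the sites imaged at both time points, and presented in random order, with scan dates and CT response withheld from the reader. Regions are placed by the same pre-set rule on both scans.

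The baseline look that footnote j needs for choosing sites stays, but its values are not used in the analysis. Cropping deals with the unequal coverage that footnote j can produce.

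Cost: a few lines of SAP text, a written region rule, and de-identified exports of at most about 15 scan pairs, all within the department already named. Lipid results come later than they would with reading as scans arrive. Masking remains imperfect when lesions visibly change size, and the report should say so.

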#### 4.7 Study Calendar

	Pre-Study	Day 1	Wk 2	Wk 4	Wk 6	Wk 8	Wk 10	Wk 12	Wk 14	Wk 16	Wk 18	Wk 20	Wk 24/ EOT	Wk 28	Post treatment
Pioglitazone a		X													
Informed consent	X														
Demographics	X														
Medical history	X														
Concurrent meds	X														
Physical exam	X							X					X		
Vital signs	X							X					X		
Height	X														
Weight b															
Performance status	X							X					X		
Serum chemistry cd	X	X g				X				X			X		
CBC d	X	X g				X				X			X		
Thyroid blood tests de	X	X g					X						X		
β-hCG df	X														
Adverse event evaluation h	X		X	X				X			X		X		X
Tumor related imaging i	X							X					X	X	
Other correlative studies j	X												X		

a: Dose per protocol; orally administered once daily for 24-28 weeks..

b: Weight obtained at each study site visit and once/week on each subject's same home scale.

c: Pre-Study and Day 1 chemistries: bicarbonate, BUN, chloride, creatinine, glucose, potassium, SGOT[AST], sodium. At weeks 8, 16, 24: glucose, AST.

d: Blood tests can be performed locally.

e: TSH, Free T4, thyroglobulin, thyroglobulin antibodies. All thyroglobulin measurements are to be performed in the same laboratory. Serum thyroglobulin will not be used as a response parameter if endogenous antibodies invalidate the measurement.

f: Pregnancy test in women of childbearing potential only.

g: Within 1 month prior to administration of protocol therapy. Pre-Study assessments if within 1 month will suffice.

h: Adverse events evaluations at weeks 2, 4, 18 and post treatment (within 4 weeks and at 6 months) will be by telephone.

i: Baseline CT or MRI scans must be done within 4 weeks prior to the start of therapy. Baseline CT includes neck, chest and abdomen. Follow-up imaging for disease response is at sites of disease detected at baseline and must include abdomen in cases of elevated AST to evaluate for liver metastases. Week 28 confirmatory CT for patients who need such for RECIST criteria confirmation. Baseline MRI includes: areas with lesions on CT for which there is reasonable diagnostic uncertainty that may be clarified by MRI; and/or brain if clinically indicated.

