## **8. MEASUREMENT OF EFFECT**

### **8.1 Antitumor Effect – Solid Tumors**

For the purposes of this study, patients should be re-evaluated for response every 12 ±1 weeks, with a confirmatory CT 4 or more weeks after the 24 week imaging if required by RECIST criteria.

Response and progression will be evaluated in this study using Response Evaluation Criteria in Solid Tumors (RECIST) 1.1.

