#### **8.1.1 Definitions**

Evaluable for toxicity. All patients will be evaluable for toxicity from the time of their first treatment with pioglitazone.

Evaluable for objective response. Only those patients who have measurable disease present at baseline (an eligibility criterion), have received at least 11 weeks of therapy and have had their disease re-evaluated; or who come off therapy due to progressive disease or unacceptable adverse events at any time, will be considered evaluable for response. These patients will have their response classified according to the definitions stated below.

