### **8.2.3 Evaluation of Best Overall Response**

The best overall response is the best response recorded from the start of the treatment until disease progression/recurrence (taking as reference for progressive disease the smallest measurements recorded since the treatment started). The patient's best response assignment will depend on the achievement of both measurement and confirmation criteria.

Target Lesions	Non-Target Lesions	New Lesions	Overall Response	Best Response for this Category Also Requires:
CR	CR	No	CR	>4 wks. confirmation
CR	Non-CR/Non-PD	No	PR	>4 wks. confirmation
PR	Non-PD	No	PR	
SD	Non-PD	No	SD	documented at least once >4 wks. from baseline

PD	Any	Yes or No	PD	no prior SD, PR or CR
Any	PD*	Yes or No	PD	
Any	Any	Yes	PD	

\* In exceptional circumstances, unequivocal progression in non-target lesions may be accepted as disease progression.

Note: Patients with a global deterioration of health status requiring discontinuation of treatment without objective evidence of disease progression at that time should be reported as "*symptomatic deterioration*". Every effort should be made to document the objective progression even after discontinuation of treatment.

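### The primary response rate omits treated patients who stop before week 11 for reasons other than progression or toxicity; no all-treated rate is planned, and evaluability is defined in two ways

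*Combined protocol and SAP*

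**What the plan says.** Section 9.2 makes the best response percentage and its 95% binomial confidence interval the primary result, in evaluable patients only. Evaluable patients have measurable disease and "have received at least 11 weeks of therapy and have had their disease re-evaluated; or who come off therapy due to progressive disease"; stopping for unacceptable toxicity also qualifies. Section 8.1.1 has the same rule, ending "or who come off therapy due to progressive disease or unacceptable adverse events at any time, will be considered evaluable for response".

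Section 9.1 is shorter: "A patient will be evaluable if they remain on treatment for 11 weeks or they are removed from study due to progression or toxicity". It does not ask for a re-evaluation.

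Section 4.3 lists further reasons for stopping: intercurrent illness, the patient's own withdrawal, and a change in condition as judged by the investigator. None of these makes a patient evaluable if it occurs before week 11.

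On assessment, section 8.1 says "patients should be re-evaluated for response every 12 ±1 weeks", and 9.2 says "Patients in response categories 1-2 while on treatment will be considered responders to treatment". Section 9.2 sorts evaluable patients into eight categories. Three are for early deaths (5 to 7) and one is for unknown response (8).

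For toxicity, 9.2 uses a wider set: "All patients enrolled and who receive any drug will be assessable for toxicity from the time of their first treatment with study drug". No response rate is planned in that set. Section 9.3 accrues 15 to secure 14, allowing for one loss.

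**The concern.** Whether a patient enters the denominator depends on what happens after treatment starts, and on how the reason for stopping is recorded. A patient who stops unscanned at week 6 for unacceptable toxicity stays in the denominator without a response. A patient who stops unscanned at week 6 by choice disappears. The trial has no control arm, so the percentage and its interval carry the whole primary result. Removing people who mostly cannot have a recorded response will usually push that percentage up.

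The two definitions raise a second question. A patient with 11 weeks of drug and no scan is in the denominator under 9.1 and out under 8.1.1 and 9.2. The category list does not settle it. An early death from a cause other than the cancer or toxicity, and an unknown response, each have a category, yet categories are assigned only to evaluable patients and the strict rule leaves little room for either.

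**Working it through.** **Inputs.** From 9.1: 14 evaluable patients, 40% target against 5% or less, two-sided 5% level, 87% power. From 9.3: 15 accrued, one loss. Assumptions: the 15 are treated patients (9.3 calls them evaluable, but someone lost before week 11 could not be); the binomial interval is Clopper-Pearson, with lower limit the 2.5% quantile of Beta(x, n − x + 1); losses above one are illustrative.

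**1. The plan's own power.** The critical count is the smallest r with P(X ≥ r | n, 0.05) ≤ 0.025.
- n = 14: P(X ≥ 3) = 0.0301, P(X ≥ 4) = 0.0042, so r = 4.
- Power = P(X ≥ 4 | 14, 0.40) = 87.6%. The stated 87% reproduces, so nothing here disputes it.

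**2. Size of the shift at one loss, 6 responders among 15 treated.**

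| Case | Evaluable rate (95% CI) | All-treated rate (95% CI) |
|---|---|---|
| Leaver is a non-responder | 6/14 = 42.9% (17.7 to 71.1) | 6/15 = 40.0% (16.3 to 67.7) |
| Leaver is one of the responders | 5/14 = 35.7% (12.8 to 64.9) | 6/15 = 40.0% (16.3 to 67.7) |

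The first case adds 2.9 points; the second removes 4.3.

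**3. Expected shift.** If the evaluable rate is 40% and each of L leavers out of 15 has probability q of a recorded response, the all-treated rate is [(15 − L) × 0.40 + Lq]/15. The evaluable rate exceeds it by L(0.40 − q)/15.

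| L | q = 0 | q = 0.1 | q = 0.2 | q = 0.4 |
|---|---|---|---|---|
| 1 | 2.7 | 2.0 | 1.3 | 0 |
| 2 | 5.3 | 4.0 | 2.7 | 0 |
| 3 | 8.0 | 6.0 | 4.0 | 0 |

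(percentage points)

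**4. Does the comparison with 5% change?** At n = 15, P(X ≥ 3) = 0.0362 and P(X ≥ 4) = 0.0055, so r is again 4.
- 14 evaluable of 15, non-responding leaver: the responder count and the threshold are the same in both sets, so nothing changes.
- 14 evaluable of 15, responding leaver: 3/14 has lower limit 4.66% and 4/15 has 7.79%. This is the only change possible at 14 evaluable, and here the plan's rule is the less favourable one.
- 13 evaluable of 15, both leavers non-responders: 3/13 has lower limit 5.04% and 3/15 has 4.33%. An upward change needs this situation: 13 or fewer evaluable and exactly 3 responders.

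**5. Power of an all-treated rate.** With 15 treated, r = 4 and non-responding losses, power is P(X ≥ 4 | 15 − L, 0.40): 87.6% for one loss, 83.1% for two, 77.5% for three.

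**The case against.** The evaluable set is prespecified, and the sample size was calculated on it. It already keeps progression and unacceptable toxicity in the denominator whenever they occur, and those are the most informative exits. A shift of 2.9 points is small beside an interval running from 17.7% to 71.1%. A reader could also divide the responders by the number treated, since toxicity is reported in that set. All of this stands. It argues against replacing the primary denominator, but not against prespecifying the second rate.

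Three stronger readings are tempting and do not hold.

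- *The exclusion can only inflate the rate.* The calendar places tumour imaging in a combined week 24 and end-of-treatment column, so an early leaver may be scanned, and a response seen then would also be dropped.
- *An early response could never qualify, because the only confirming scan follows week 24.* Section 8.2.3 does say "best response assignment will depend on the achievement of both measurement and confirmation criteria", and calendar note i provides a "Week 28 confirmatory CT for patients who need such for RECIST criteria confirmation". But 4.3 also describes a week 12 response confirmed at week 24. The partial-response, non-progressing row of the 8.2.3 table shows no confirmation entry in the available text, possibly because of a merged cell. A patient gone before week 11 would rarely have a later confirming scan; the documents support no more than that.
- *A patient with 11 weeks and no scan is certainly excluded.* Section 9.1 counts that patient, and 9.2 has an unknown category. The documents conflict.

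**Conclusion.** The point holds at minor severity. Treated patients who stop before week 11 for reasons other than progression or unacceptable toxicity leave the primary denominator, and 9.2 plans no rate that includes them. The effect is usually upward when there is at least one responder. With 6 responders it is 2.9 points at the one loss in 9.3, and larger only if losses exceed what the documents state. This rests on early leavers seldom having a recorded response, which follows from the week 12 ±1 scan but is not guaranteed.

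A reader might infer that the rule could make an inactive drug look active. At the planned single loss it cannot do so by dropping a non-responder, since 4 responders are needed at both 14 and 15. An upward change takes at least two losses and exactly 3 responders, with lower limits of 5.04% and 4.33% on either side of 5%.

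Separately, 9.1 conflicts with 8.1.1 and 9.2 on the re-evaluation condition, and categories 7 and 8 fit poorly with the strict rule.

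**What to change.** In 9.2, keep the evaluable-set rate and add a second prespecified rate beside it, for example: *The response rate will also be reported with an exact 95% confidence interval in all enrolled patients who receive any study drug. Anyone without a complete or partial response under section 8.2 is counted as a non-responder.* This is the set 9.2 already uses for toxicity, so it needs no further eligibility filter.

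Use one evaluability definition in 8.1.1, 9.1 and 9.2, stating whether re-evaluation is required, and say how categories 5 to 8 enter each denominator.

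The cost is a few sentences and a second, usually slightly lower, reported rate. No new data are needed and the primary sample size is unaffected. With 15 treated and one non-responding loss, the all-treated rate has 87.6% power, in line with the stated 87%.
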